9.3. Recording and Follow-Up of Adverse Events and/or Serious Adverse Events

Adverse Event and Serious Adverse Event Recording

- An AE/SAE that begins or worsens after informed consent is signed should be recorded on the Adverse Event Form in the eCRF. Conditions that were present at the time informed consent was given should be recorded on the Medical History Form in the eCRF.
- When an AE/SAE occurs, it is the responsibility of the investigator to review all documentation (eg, hospital progress notes, laboratory reports, and diagnostics reports) related to the event.
- The investigator (or delegate) will then record all relevant AE/SAE information in the eCRF.
- It is **not** acceptable for the investigator to send photocopies of the participant's medical records in lieu of completing the AE eCRF page.
- There may be instances when copies of medical records for certain cases are requested. In this case, all participant identifiers, with the exception of the participant number, will be redacted on the copies of the medical records before submission.
- The investigator will attempt to establish a diagnosis of the event based on signs, symptoms, and/or other clinical information. Whenever possible, the diagnosis (not the individual signs/symptoms) will be documented as the AE/SAE. When a clear diagnosis cannot be identified, each sign or symptom should be reported as a separate AE/SAE.

To the extent possible, each AE/SAE should be evaluated to determine:

- The severity grade (CTCAE Grade 1 to 5). See below for further instructions on the assessment of intensity.
- Whether there is at least a reasonable possibility that the AE is related to the study drug: suspected (yes) or not suspected (no). See below for further instructions on the assessment of causality.
- The start and end dates, unless unresolved at final follow-up.
- The action taken with regard to study drug as a result of the AE/SAE(s).

- The event outcome (eg, not recovered/not resolved, recovered/resolved, recovering/resolving, recovered/resolved with sequelae, fatal, unknown).
- The seriousness, as per the SAE definition provided in Section 9.2.
- The action taken with regard to the event. Note: If an AE is treated with a concomitant medication or nondrug therapy, this action should be recorded on Adverse Event Form and the treatment should be specified on the appropriate eCRF (eg, Prior/Concomitant Medications, Procedures and Non-Drug Therapy).

Assessment of Intensity

The severity of AEs will be assessed using CTCAE v4.03 Grades 1 through 5. If an event is not classified by CTCAE, the severity of the AE will be graded according to the scale below to estimate the grade of severity:

The investigator will make an assessment of intensity for each AE and SAE reported during the study and assign it to 1 of the following categories:

- **Grade 1:** Mild; asymptomatic or mild symptoms; clinical or diagnostic observations only; treatment not indicated.
- **Grade 2:** Moderate; minimal, local, or noninvasive treatment indicated; limiting age appropriate activities of daily living.
- **Grade 3:** Severe or medical significant but not immediately life-threatening; hospitalization or prolongation of hospitalization indicated; disabling; limiting self-care activities of daily living.
- **Grade 4:** Life-threatening consequences; urgent treatment indicated.
- **Grade 5:** Fatal.

Assessment of Causality

- The investigator is obligated to assess the relationship between study treatment and each occurrence of each AE/SAE.
- A "reasonable possibility" of a relationship conveys that there are facts, evidence, and/or arguments to suggest a causal relationship, rather than that a relationship cannot be ruled out.
- The investigator will use clinical judgment to determine the relationship.
- The investigator will also consult the RSI in the IB and/or Product Information, for marketed products, in his/her assessment.
- Alternative causes, such as underlying disease(s), concomitant therapy, and other risk factors, as well as the temporal relationship of the event to study treatment administration, will be considered and investigated.
- For each AE/SAE, the investigator **must** document in the medical notes that he/she has reviewed the AE/SAE and has provided an assessment of causality.
- With regard to assessing causality of SAEs:
 - There may be situations in which an SAE has occurred and the investigator has minimal information to include in the initial report. However, the causality assessment is one of the criteria used when determining regulatory reporting requirements. **Therefore, it is very important that the investigator always make an assessment of causality for every event before the initial transmission of the SAE.**
 - The investigator may change his/her opinion of causality in light of follow-up information and send a follow-up SAE report with the updated causality assessment.

Follow-Up of Adverse Events and Serious Adverse Events

- The investigator is obligated to perform or arrange for the conduct of supplemental measurements and/or evaluations as medically indicated or as requested by the sponsor to elucidate the nature and/or causality of the AE or SAE as fully as possible. This may include additional laboratory tests or investigations, histopathological examinations, or consultation with other health care professionals.
- If a participant dies during participation in the study or during a recognized follow-up period, the investigator will provide the sponsor with a copy of any postmortem findings, including histopathology.
- New or updated information will be recorded in the originally completed eCRF.
- Any updated SAE data will be submitted to the sponsor (or designee) within 24 hours of receipt of the information.
- Once an AE is detected, it should be followed until it has resolved or until it is judged to be permanent; assessment should be made at each visit (or more frequently if necessary) of any changes in severity, the suspected relationship to the study drug, the interventions required to treat the event, and the outcome.
- When the severity of an AE changes over time for a reporting period (eg, between visits), each change in severity will be reported as a separate AE until the event resolves.

9.4. Reporting of Serious Adverse Events

All SAEs, regardless of suspected causality (eg, relationship to study drug, or study procedure[s]), occurring after the participant has signed the ICF through the last study visit or 30 + 7 days after the last dose of study drug, whichever occurs later, must be reported to the sponsor (or designee) within **24 hours** of learning of its occurrence, unless otherwise specified by the Protocol. The investigator will submit any updated SAE data to the sponsor (or designee) within 24 hours of it being available.

Investigators are not obligated to actively seek AE or SAE information after conclusion of the study participation. However, if the investigator learns of any SAE, including a death, at any time after a participant has been discharged from the study, and he/she considers the event to be reasonably related to the study treatment or study participation, the investigator must notify the sponsor (or designee) within 24 hours of becoming aware of the event.

After the initial AE/SAE report, the investigator is required to proactively follow each participant at subsequent visits/contacts. All SAEs will be followed until resolution, stabilization, the event is otherwise explained, or the participant is lost to follow-up (as defined in Section 7.3).

Prompt notification by the investigator to the sponsor of a SAE is essential so that legal obligations and ethical responsibilities towards the safety of participants and the safety of a study treatment under clinical investigation are met.

If the SAE is not documented in the **IB** for the study drug (new occurrence) and is thought to be related to the sponsor's study drug, the sponsor or its designee may urgently require further information from the investigator for reporting to health authorities. The sponsor or its designee may need to issue an Investigator Notification to inform all investigators involved in any study with the same drug that this SAE has been reported. Suspected Unexpected Serious Adverse Reactions will be collected and reported to the competent authorities and relevant ethics committees in accordance with Directive 2001/20/EC, or as per national regulatory requirements in participating countries.

The sponsor has a legal responsibility to notify both the local regulatory authority and other regulatory agencies about the safety of a study treatment under clinical investigation. The sponsor will comply with country-specific regulatory requirements relating to safety reporting to the regulatory authority, IRB/IEC, and investigators.

Investigator safety reports must be prepared for suspected unexpected adverse reactions according to local regulatory requirements and sponsor policy and forwarded to investigators as necessary.

An investigator who receives an investigator safety report describing a SAE or other specific safety information (eg summary or listing of SAEs) from the sponsor will review and then file it along with the Investigator's Brochure and will notify the IRB/IEC, if appropriate according to local requirements.

Serious Adverse Event Reporting

- Information about all SAEs is collected and recorded on the Adverse Event Form in the eCRF.
- The investigator must also complete the Incyte Serious Adverse Event Report Form, in English. Refer to the Incyte Reference Guide for Completing the Serious Adverse Event Report Form.
- Facsimile or email transmission of the Serious Adverse Event Report Form is the preferred method to transmit this information to Pharmacovigilance/designee (eg, C3i/Telerx). The contact information of the sponsor's study-specific representatives is listed in the Study Manual provided to each site. The original copy of the Serious Adverse Event Report Form and the confirmation sheet must be kept at the study site.
-
- Follow-up information is recorded on an amended or new Serious Adverse Event Report Form, with an indication that it is follow-up to the previously reported SAE and the date of the original report. The follow-up report should include information that was not provided on the previous Serious Adverse Event Report Form, such as the outcome of the event (eg, resolved or ongoing), treatment provided, action taken with study drug because of the SAE (eg, dose reduced, interrupted, or discontinued), or participant disposition (eg, continued or withdrew from study participation). Each recurrence, complication, or progression of the original event should be reported as follow-up to that event, regardless of when it occurs.
- In rare circumstances, and in the absence of facsimile or computer equipment, notification by telephone is acceptable with a copy of the Incyte Serious Adverse Event Report Form sent by overnight mail or courier service. Initial notification via telephone does not replace the need for the investigator to complete and sign the Serious Adverse Event Report Form within the designated reporting time frames.
- Contacts for SAE reporting can be found in the Study Manual.

9.5. Adverse Events of Special Interest

Adverse events of special interest are defined as occurrences of PJP or other serious infections due to bacterial, mycobacterial, invasive fungal, viral, or other opportunistic pathogens; colitis; and exfoliative dermatitis.

9.6. Emergency Unblinding of Treatment Assignment

Not applicable.

9.7. Pregnancy

Pregnancy, in and of itself, is not regarded as an AE unless there is suspicion that study drug may have interfered with the effectiveness of a contraceptive medication or method. When a pregnancy has been confirmed in a participant during maternal or paternal exposure to study drug, the following procedures should be followed in order to ensure safety:

- The study drug must be discontinued immediately.
- The investigator must complete and submit the Incyte Clinical Trial Pregnancy Form to the sponsor or its designee within **24 hours** of learning of the pregnancy.

Data on fetal outcome are collected for regulatory reporting and drug safety evaluation. Follow-up should be conducted for each pregnancy to determine outcome, including spontaneous or voluntary termination, details of the birth, and the presence or absence of any birth defects, congenital abnormalities, or maternal and/or newborn complications, by following until the first well-baby visit. Pregnancy should be recorded on a Clinical Trial Pregnancy Form and reported by the investigator to the sponsor or its designee. Pregnancy follow-up information should be recorded on the same form and should include an assessment of the possible causal relationship to the sponsor's study drug to any pregnancy outcome, as well as follow-up to the first well-baby visit or the duration specified in local regulations, whichever is later. Refer to the Incyte Reference Guide for Completing the Clinical Trial Pregnancy Form.

Any SAE occurring during pregnancy of a study participant must be recorded on the Serious Adverse Event Report Form and submitted to the sponsor or designee.

Abnormal pregnancy outcomes (eg, spontaneous abortion, fetal death, stillbirth, congenital anomalies, or ectopic pregnancy) are considered SAEs (if occurring in the study participant) and must be reported as described in Section 9.4. If an abnormal pregnancy outcome is reported in a study participant's partner, the event should be reported to the sponsor on the Clinical Trial Pregnancy Form.

9.8. Warnings and Precautions

Special warnings or precautions for the study drug, derived from safety information collected by the sponsor or its designee, are presented in the **IB**. Additional safety information collected between IB updates will be communicated in the form of Investigator Notifications. Any important new safety information should be discussed with the participant during the study, as necessary. If new significant risks are identified, they will be added to the ICF.

9.9. Product Complaints

The sponsor collects product complaints on study drugs and drug delivery systems used in clinical studies in order to ensure the safety of study participants, monitor quality, and facilitate process and product improvements.

All product complaints associated with material packaged, labeled, and released by the sponsor or its designee will be reported to the sponsor. All product complaints associated with other study material will be reported directly to the respective manufacturer.

The investigator or his/her designee is responsible for reporting a complete description of the product complaint via email or other written communication to the sponsor contact or respective manufacturer as noted in the packaging information. Any AE associated with a product complaint should be recorded as described in Section 9.3.

If the investigator is asked to return the product for investigation, he/she will return a copy of the product complaint communication with the product.

9.10. Treatment of Overdose

There has been no clinical experience with overdose of INCB050465. Treatment of overdose should consist of general supportive measures.

10. STATISTICS

10.1. Sample Size Determination

The sample size is based on the demonstration of preliminary findings of efficacy, which also depends on the occurrence of safety findings. Approximately 12 participants will be enrolled, which will provide > 90% chance of detecting at least 1 AE of interest (eg, platelets, hemoglobin, ANC, liver functions, and infections) if the underlying AE rate is 20%.

10.3. Level of Significance

No formal efficacy hypotheses will be tested.

10.4. Statistical Analyses

Both efficacy and safety analyses will be conducted using the FAS. The baseline value for a variable will be defined as the last nonmissing value for the variable before or on Day 1, unless otherwise specified.

10.4.1. Efficacy Analysis

Efficacy assessments will be summarized using descriptive statistics at each visit.

For the primary endpoint, proportion of participants with 1 point or greater improvement on the SGUS for parotid and submandibular glands, as well as the secondary endpoint of PGIC, summary statistics will include sample size, frequency, and percentages.

For all other measurements in the secondary endpoints, which are continuous, summary statistics will include sample size, mean, median, standard deviation, standard error of the mean, minimum, maximum, and the 95% confidence interval where appropriate. Summary statistics will be provided for baseline, the actual measurements at each visit, and the change and percent change from baseline at each visit, if applicable. All analyses will be implemented using SAS version 9.1 or higher.

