8.2.4.5. PROMIS Fatigue Short Form

The PROMIS fatigue short form includes 7 items with a rating scale of 1 to 5. The recall period is 7 days.

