8.2.4.6. European Quality Of Life 5 Dimensions Questionnaire

The EQ-5D is a standardized measure of health status. It consists of 5 questions, each with a 5-item rating scale plus a visual analog scale rating from 1 to 100 for overall health status. The questionnaire probes the participants responses for the current day.

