7.2. Analysis of Efficacy Endpoints

The efficacy endpoints include the following:

- Proportion of participants with a 1 point or greater improvement on the SGUS score for parotid and submandibular glands at Week 4 and Week 12.
- Change and percentage change in SGUS score from baseline at Week 4 and Week 12.
- Change and percentage change in stimulated and unstimulated whole salivary flow from baseline at Weeks 4, 8, and 12.
- Change and percentage change in ESSDAI at Week 12.
- Change and percentage change in ESSPRI at Weeks 4, 8, and 12.
- Change and percentage change in symptom scores for dryness of eyes, mouth, and vagina and in total symptom scores in female at Weeks 4, 8, and 12.
- Proportions of participants in each PGIC category at Weeks 4, 8, and 12.
- Change and percentage change in PROMIS Fatigue short form at Weeks 4, 8, and 12.
- Change and percentage change in FSFI at Weeks 4, 8, and 12 (female participants only).
- Change and percentage change in EQ-5D at Weeks 4, 8, and 12.

Category variables will be summarized using descriptive statistics including sample size, frequency, and percentages. Continuous variables will be summarized using descriptive statistics including sample size, mean, median, standard deviation, minimum, and maximum. For endpoints with clinically meaningful subscores, these subscores will also be summarized.

[REDACTED]

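### Percent change is planned for EQ-5D and PROMIS Fatigue with no score named; on item levels or a raw sum, its value depends on how the answers are coded

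*Protocol*

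**What the plan says.** Protocol 10.4.1 sorts the efficacy endpoints into two types.

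- **Frequencies.** The primary SGUS responder proportion is handled this way, "as well as the secondary endpoint of PGIC, summary statistics will include sample size, frequency, and percentages".
- **Continuous.** Everything else: "For all other measurements in the secondary endpoints, which are continuous, summary statistics will include sample size, mean, median, standard deviation". The same paragraph adds summaries of "the change and percent change from baseline at each visit, if applicable". It does not say when percent change applies.

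The instruments are described as follows, in the same terms in the protocol and the SAP.

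- **EQ-5D** (Protocol 8.2.4.6, SAP 7.1.4.6): "It consists of 5 questions, each with a 5-item rating scale plus a visual analog scale rating from 1 to 100 for overall health status".
- **PROMIS Fatigue** (Protocol 8.2.4.5, SAP 7.1.4.5): "The PROMIS fatigue short form includes 7 items with a rating scale of 1 to 5".

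SAP 7.2 lists "Change and percentage change in EQ-5D at Weeks 4, 8, and 12" and "Change and percentage change in PROMIS Fatigue short form at Weeks 4, 8, and 12". Protocol Table 5 and SAP Table 1 carry matching endpoint lines. SAP 7.2 does not repeat the statement that these endpoints are continuous. It has a general frequency rule for categorical variables and a rule that clinically meaningful subscores are also summarised, but it assigns neither instrument to either rule. SAP Appendix A plans one EQ-5D table (2.1.9) and one PROMIS table (2.1.7), with no component named. SAP 10.1 records no change from the protocol's analyses.

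**The concern.** PGIC, a single question with seven ordered answers, is treated as categorical. The EQ-5D questions, with five answers each, fall under the continuous rule, and no reason is given for the difference. EQ-5D as described has six components, and the endpoint lines do not say which of them, or what combination, is to be analysed.

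Percent change needs a meaningful zero. An answer level coded 1 to 5 has none, and neither does a sum of seven items each scored at least 1. A percent change on such a number is partly a property of the code. It is also asymmetric: one step up from level 1 and one step back down do not cancel.

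The study has one arm and about 12 participants. There is no comparator in which the same artefact would appear and cancel, and one or two participants can move a mean percent change. If the score is chosen after open-label data have been seen, the choice is also open to influence by the results.

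**Working it through.** **Plan's own figure.** The documents give no figure for these endpoints. Their only design calculation is the chance of at least one adverse event of interest with 12 participants at a 20% rate. It reproduces as 1 - 0.8^12 = 93.1%, against the stated value above 90%. It has no bearing on this point.

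**Inputs from the documents.** Seven PROMIS items rated 1 to 5; five EQ-5D questions with five answers each; a VAS from 1 to 100; about 12 participants.

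**Assumptions, because the documents give no scoring rule or data.** PROMIS is scored as a raw sum, EQ-5D answers are coded 1 to 5, and all baseline and follow-up values are illustrative. Percent change = 100 × (follow-up - baseline) / baseline.

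**1. PROMIS raw sum.** Coded 1 to 5, the sum runs from 7 × 1 = 7 to 7 × 5 = 35. Coded 0 to 4, the same answers score 7 points lower, from 0 to 28.

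| Same answers, sum coded 1 to 5 | Absolute change, either coding | Percent change, coded 1 to 5 | Percent change, coded 0 to 4 |
|---|---|---|---|
| 21 to 14 | -7 | -7/21 = -33.3% | -7/14 = -50.0% |
| 14 to 7 | -7 | -7/14 = -50.0% | -7/7 = -100.0% |
| 35 to 7 | -28 | -28/35 = -80.0% | -28/28 = -100.0% |

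Absolute change is the same under both codings; percent change is not. With 1-to-5 coding, even a move from the worst possible score to the best possible score stops at -80%.

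**2. EQ-5D item, effect of origin.** Level 3 to 2 is -1/3 = -33.3% on codes 1 to 5 and -1/2 = -50.0% on codes 0 to 4. A participant who starts at the best level has no defined percent change on codes 0 to 4, because the baseline is zero.

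**3. EQ-5D item, balanced movement on codes 1 to 5.**

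- One participant moves from 1 to 2 (+100%) and one from 2 to 1 (-50%). Mean change is 0; mean percent change is (100 - 50)/2 = +25%.
- The same swap between levels 2 and 3 gives (50 - 33.3)/2 = +8.3%.
- With one 1-2 swap and the other 10 of 12 participants unchanged, mean percent change is (100 - 50)/12 = +4.2% and mean change is still 0.
- Assume a stable distribution over levels 1 to 5 of 30/30/25/10/5%, with equal traffic each way between neighbouring levels at a fraction r of the smaller group. Mean percent change is r × [0.30 × (1 - 1/2) + 0.25 × (1/2 - 1/3) + 0.10 × (1/3 - 1/4) + 0.05 × (1/4 - 1/5)] = r × 0.2025. For r from 0.1 to 0.3 that is +2.0% to +6.1%, with mean change 0.

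**4. EQ-5D item, effect of spacing on mean change.** Let 7 participants worsen from level 2 to 3 and 5 improve from 5 to 4. On codes 1, 2, 3, 4, 5 mean change is (7 × 1 - 5 × 1)/12 = +0.167. On codes 1, 2, 3, 5, 9 it is (7 × 1 - 5 × 4)/12 = -1.083. For single items, then, even the sign of the mean change can depend on the spacing given to the levels.

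**5. VAS.** From 50 to 60 is +20.0%, or 10/49 = +20.4% if the scale began at 0 instead of 1. From 20 to 30 is +50.0% or 10/19 = +52.6%. The origin matters little here.

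**The case against.** The strongest reply is that the documents do not commit to the harmful calculation. A reader might infer that raw EQ-5D level codes will be averaged, so that the planned means and percent changes simply reflect level coding. The text does not support that. It lists the components and says only that change in EQ-5D will be summarised, which could mean the VAS, an index or the items. The table shells are in a separate document, and SAP 7.2 ends in a redaction. This part of the objection stands: the documented fault is a percent-change plan for an unnamed score.

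The reply also points to softening text: the qualifier in 10.4.1, and the SAP rules for categorical variables and subscores, which leave room to tabulate EQ-5D items by frequency. They do leave room, but nothing assigns EQ-5D or PROMIS to those rules, and the endpoint lines name percent change for both instruments outright.

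Third, the consequences are limited. No hypotheses are tested, no p-values are given, absolute change is summarised beside percent change, and Listings 2.6.7 and 2.6.9 cover both instruments. In the swap example the same summary would show a mean change of 0. This also stands, and it is why the point is minor. The level distribution and traffic rates in the working are assumptions. With 12 participants, 10% traffic between levels 1 and 2 is 0.1 × 0.30 × 12 = 0.36 of a participant each way, so those figures illustrate the mechanism and do not predict the result.

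**Conclusion.** The point holds in a limited form and is minor. The protocol applies a continuous-data rule to every secondary endpoint except PGIC, and both documents plan percent change for two instruments whose analysed score is not named. If EQ-5D item levels or a PROMIS raw sum are used, percent change depends on the coding: -33.3% or -50.0% for the same PROMIS answers, and +25% for a balanced two-person EQ-5D swap with no mean change. These sizes rest on the assumed codes and illustrative scores.

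Three stronger readings are not supported.

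- A reader might infer that PROMIS means are also distorted. They are not: shifting the origin leaves absolute change as it was.
- A reader might infer that PROMIS percent change understates improvement. That would require one origin to be the true one, and the difficulty is that none is. The result is not unique, but no direction of bias is shown.
- A reader might infer that the artefact would be taken for a drug effect. Nothing in the documents shows this, given the absolute change reported alongside.

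The VAS can reasonably be treated as continuous. The primary endpoint is unaffected, and Protocol Table 1 lists only salivary CXCL13 and safety as key secondary.

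**What to change.** In SAP 7.2, and in Protocol 10.4.1 at the next amendment:

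- Summarise each of the five EQ-5D dimensions as number and percentage at each level at baseline and Weeks 4, 8 and 12, with number and percentage better, the same or worse than baseline.
- Report the VAS separately, as a continuous change. If an EQ-5D index is also intended, name it and its scoring.
- Name the PROMIS Fatigue score and its scoring rule, and report absolute change only.
- Drop percent change for the EQ-5D dimensions and PROMIS Fatigue.
- Bring the endpoint lines in SAP Table 1 and Protocol Table 5 into line, record the departure in SAP 10.1, and update Tables 2.1.7 and 2.1.9.

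**Cost.** The completed questionnaires already go into the eCRF (Protocol 8.2.4), so no new data, visits or participants are needed. Two percent-change summaries named in the endpoint tables are given up, two table shells change, and the SAP needs a revised version. The protocol edits can wait for an amendment made for other reasons, since amendments go through ethics review (Protocol 11.1). The scores should be fixed before the open-label data are summarised.
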